14.1 Columbia University Medical Center, New York, US

14.1.1 *Form FDA 1572*

Prior to initiating this study, the Chief Investigator and the Principal Investigator at the Participating Organization(s) will provide a signed Form FDA 1572 stating that the study will be conducted in compliance with regulations for clinical investigations and listing the investigators that will participate in the protocol.

14.1.2 *Other required documents*

- Signed and dated current (within two years) CV or short biography for all investigators listed on the Form FDA 1572 for the Lead Organization and all Participating Organizations.
- Current medical licenses for all investigators listed on Form FDA 1572 for the Lead Organization and all Participating Organizations.
- Laboratory certification (eg, CLIA, CAP) and laboratory normal ranges for all labs listed on Form FDA 1572 for the Lead Organization and all Participating Organizations.
- IRB Membership list/letter from IRB for the Lead Organization and all Participating Organizations.
- Documentation of training in “Protection of Human Research Subjects” for all investigators listed on the FDA Form 1572 for the Lead Organization and all Participating Organizations.
- Documentation of Federal-wide Assurance (FWA) number for the Lead Organization and all Participating Organizations.
- Signed receipt of Investigator Brochure

- Delegation of Responsibility form
- FDA Form 3455 Financial Disclosure Form
- Evidence of submission of this protocol to the FDA

14.1.3 ***Institutional Review Board (IRB) approval***

Prior to initiating the study and receiving study medication, the Investigators at the Lead Organization and the Participating Organization(s) will obtain written approval to conduct the study from the appropriate IRB. Should changes to the study become necessary, protocol amendments will be submitted to the respective institutional IRBs.

14.2 **National Institute for Health Research Clinical Investigation Ward, Cambridge, UK**

The trial protocol will be reviewed by a recognised REC, the Scientific Advisory Board (SAB) at Addenbrooke's Clinical Research Centre, and by the MHRA. The trial will not proceed in the UK unless the sponsor obtains from the MHRA a clinical trial authorisation (CTA), and the main REC and SAB approves the trial. The trial will not proceed until the local National Health Service Trust has approved it.

The trial will be done in compliance with EU Directives 2001/20/EC and 2005/28/EC, The Medicines for Human Use (Clinical Trials) Regulations 2004 and current amendments, the Declaration of Helsinki (South Africa Revision, 1996), GMP, the standard operating procedures issued by NRES for RECs in the UK, and Good Clinical Practice.

The sponsor will ensure that the MHRA and the REC are informed promptly of suspected serious adverse reaction (SUSARs), and that any new reports of SUSARs from other ongoing trials of the IMP under investigation in this trial are notified to the MHRA, and to the REC, if applicable. The sponsor will provide the investigator, the REC and the MHRA with annual safety reports of each IMP under investigation, and listings of all SSAR reports.

The investigator will promptly inform the sponsor and chief investigator of any SAE that occurs during this trial. The principal investigator will in turn inform the REC, if applicable. The principal investigator will provide the REC with annual progress reports of the trial, if it lasts longer than a year.

The principal investigator will report to the sponsor and chief investigator any protocol deviation that is, in his or her opinion, of clinical significance. The principal investigator will also inform the sponsor and chief investigator in the event of several deviations which, although of no clinical significance, cause inconvenience and/or discomfort to the volunteers. The principal investigator will in turn promptly inform the REC.

The sponsor will notify the MHRA and REC of any serious breach of Good Clinical Practice (for example, the investigator puts subjects' safety at risk, falsifies data, or persistently fails to comply with this protocol or Good Clinical Practice).

Within 90 days after the end of the trial, the sponsor will ensure that the REC and the MHRA are notified that the trial has finished. If the trial is terminated prematurely, those reports will be made within 15 days after the end of the trial.

The sponsor will supply a summary report of the clinical trial to the MHRA and REC within 1 year after the end of the trial.

14.3 Informed consent

All potential study participants will be given a copy of the IRB- or REC-approved information and consent form (ICF) to review. The investigator will explain all aspects of the study in lay language and answer all questions regarding the study. If the patient decides to participate in the study, he/she will be asked to sign and date the ICF. The study medication will not be released to a patient who has not signed the Informed Consent document. Patients who refuse to participate or who withdraw from the study will be treated without prejudice.

Prior to study initiation, the site-specific ICFs will be reviewed and approved by the IRB or REC, as appropriate. Prior to implementation, any changes to the ICF for Columbia University will be approved by the IRB, and any substantial changes to the ICF for Cambridge University will be approved by the REC.

15 Financing, expenses, and/or insurance

The baseline endoscopy and biopsies are considered standard of care for eligible study patients, so the cost of those procedures will not be covered by the trial. At CUMC, the baseline endoscopy and biopsies will be billed to the study patients' insurance. All additional tests and procedures, including the endoscopies and biopsies at the Week 12 visit, will be covered by the trial. The YF476 and placebo capsules will be provided free of charge. If the participant is injured and requires medical treatment as a direct result of taking part in this study, the study sponsor will pay reasonable medical costs (doctor's fees and medical expenses) needed to treat the injury. The treatment must be authorized by the investigator except in the event of an emergency in which case the investigator should be notified as soon as possible.

16 Obligations of the sponsor and investigator

16.1 Publication

Each party will allow the other 30 days to comment before any results are submitted for publication, or 10 days prior to an abstract presentation. Authorship should reflect work

done by the investigators and personnel of the sponsor, in accordance with generally recognized principles of scientific collaboration.

16.2 Archiving

The sponsor and both principal investigators will keep the following in a trial master file.

- All the essential documents required by GCP
- All data generated during the study

All documents will be stored such that they are readily available for inspection at the request of the sponsor or a regulatory authority. Any transfer of ownership of the investigator's data or documents will be documented, and the sponsor will be informed.

For at least 15 years after the end of the study, and at least 2 years after the last approval of a marketing application in an ICH region and until there are no pending or contemplated marketing applications in an ICH region or at least two years have elapsed since the formal discontinuation of clinical development of the study medication:

- HMR will ensure that the sponsor's master file and original copies of CRFs will be archived in a secure place; and
- the investigators will ensure that the investigator's master file, and original source documents (other than CRFs) will be archived in a secure place.

Appendix A – performance status criteria

ECOG performance status scale		Karnofsky performance scale	
Grade	Descriptions	Percent	Description
0	Normal activity. Fully active, able to carry on all pre-disease performance without restriction.	100	Normal, no complaints, no evidence of disease.
		90	Able to carry on normal activity; minor signs or symptoms of disease.
1	Symptoms, but ambulatory. Restricted in physically strenuous activity, but ambulatory and able to carry out work of a light or sedentary nature (eg, light housework, office work).	80	Normal activity with effort; some signs or symptoms of disease.
		70	Cares for self, unable to carry on normal activity or to do active work.
2	In bed <50% of the time. Ambulatory and capable of all self-care, but unable to carry out any work activities. Up and about more than 50% of waking hours.	60	Requires occasional assistance, but is able to care for most of his/her needs.
		50	Requires considerable assistance and frequent medical care.
3	In bed >50% of the time. Capable of only limited self-care, confined to bed or chair more than 50% of waking hours.	40	Disabled, requires special care and assistance.
		30	Severely disabled, hospitalization indicated. Death not imminent.
4	100% bedridden. Completely disabled. Cannot carry on any self-care. Totally confined to bed or chair.	20	Very sick, hospitalization indicated. Death not imminent.
		10	Moribund, fatal processes progressing rapidly.
5	Dead	0	Dead

Appendix B – drug interactions

Non-clinical studies support administration of the study medication (YF476) to humans for up to 13 weeks. *In vitro* studies showed that YF476 inhibited CYP2C8 and CYP3A4/5. Specific notation will be made of any regular concomitant medications metabolized via CYP2C8 or CYP3A4/5. These medications do not need to be discontinued, although specific monitoring for side effects and toxicities will be performed during the study period.

CYP 450 enzymes

In tests for reversible inhibition of CYP 450 enzymes, the IC_{50} of YF476 was 3.52, 8.37 and 12.1 μM for CYP2C8, CYP3A4 (midazolam) and CYP3A4 (testosterone), respectively. But, YF476 did not inhibit CYP2C9 at doses up to 25 μM . In tests for irreversible inhibition, 0.5 μM YF476 did not cause significant inhibition of CYP3A4 (midazolam). However, 5 μM YF476 caused 43.9% irreversible inhibition of CYP3A4 (midazolam), which was reduced to 30.2% when corrected for vehicle control. Neither CYP3A4 (testosterone) nor CYP2C9 was inhibited by 5 μM YF476. For further details of the *in vitro* studies, see the YF476 Investigator's Brochure.

To assess the likelihood of CYP2C8 and CYP3A4 inhibition in patients *in vivo*, $[I]/K_i$ ratios (where $K_i = IC_{50}/2$, and $I = C_{\text{max}}$ for YF476) were calculated from IC_{50} values for reversible inhibition by YF476 and C_{max} for total (bound and unbound) plasma concentrations of YF476 from a study of single doses of 50, 100, 200 and 400 mg in healthy subjects (Table 2. T-011; see Investigators' Brochure). FDA guidelines (2006) state that an interaction is likely if the ratio is greater than 1, possible if between 1 and 0.1, and remote if less than 0.1.

Table 2: $[I]/K_i$ ratios calculated with total (bound plus unbound) plasma concentrations of YF476.

Isoform	IC_{50} (μM)	K_i	$[I1]/K_i$	$[I2]/K_i$	$[I3]/K_i$	$[I4]/K_i$
CYP2C8	3.52	1.76	0.184	0.302	0.584	0.803
CYP3A4 (testosterone)	12.1	6.05	0.054	0.088	0.170	0.233
CYP3A4 (midazolam)	8.37	4.185	0.077	0.127	0.246	0.338

Where $K_i = IC_{50}/2$, and I_1, I_2, I_3 and $I_4 = C_{\text{max}}$ for 50, 100, 200 & 400 mg YF476, respectively, in fasting subjects.

Therefore, the likelihood of a drug-drug interaction in patients *in vivo* is:

- CYP2C8: possible for 50–400 mg YF476
- CYP3A4 (testosterone): remote for 50 & 100 mg YF476, and possible for 200 & 400 mg
- CYP3A4 (midazolam): remote for 50 mg YF476, and possible for 100–400 mg.

Although YF476 caused some irreversible inhibition of CYP3A4, the degree of inhibition makes a drug-drug interaction in patients *in vivo* unlikely.

Many medicines are metabolised via CYP3A4/5 (Dressler *et al* 2000). Very few are metabolised via CYP2C8. Examples of the main types of medicine that are metabolised by CYP3A4/5 and CYP2C8, and guidance about assessing the risk and managing drug-drug interactions is provided here.

The Table 3 lists drugs with effects on the human cytochrome P450 system. There is evidence, for drugs in this table, that these are metabolized, at least in part, via that isoform. This does not indicate that changes in the rate of that metabolic reaction will largely affect the drug's pharmacokinetics.

Table 3: Drug Interactions with cytochrome P450 system

	CYP2C8	CYP3A4/5		
Substrates	paclitaxel torsemide amodiaquine cerivastatin repaglinide	Macrolide antibiotics: clarithromycin erythromycin (not 3A5) NOT azithromycin telithromycin Anti-arrhythmics: quinidine_3OH (not 3A5) Benzodiazepines: alprazolam diazepam_3OH midazolam triazolam	HMG CoA Reductase Inhibitors: atorvastatin cerivastatin lovastatin NOT pravastatin Simvastatin Steroid 6beta-OH: estradiol hydrocortisone progesterone testosterone Prokinetic: Cisapride Calcium Channel Blockers: amlodipine diltiazem felodipine lercanidipine nifedipine2 nisoldipine nitrendipine verapamil	Immune Modulators: cyclosporine tacrolimus (FK506) HIV Antivirals: indinavir nelfinavir ritonavir saquinavir Antihistamines: astemizole chlorpheniramine terfenadine

	CYP2C8	CYP3A4/5	
		Miscellaneous:	fentanyl
		alfentanyl	finasteride
		aprepitant	gleevec
		aripiprazole	haloperidol
		bupirone	irinotecan
		cafergot	LAAM
		caffeine_TMU	lidocaine
		cilostazol	methadone
		cocaine	nateglinide
		codeine-	ondansetron
		Ndemethylation	pimozide
		dapsone	propranolol
		dexamethasone	quetiapine
		dextromethorphan	quinine
		docetaxel	
		domperidone	
		eplerenone	
Inhibitors	gemfibrozil	HIV Antivirals:	aprepitant
	trimethoprim	indinavir	erythromycin
	glitazones	nelfinavir	fluconazole
	montelukast	ritonavir	grapefruit juice
	quercetin		verapamil
			diltiazem
		clarithromycin	cimetidine
		itraconazole	diethyldithiocarbamate
		ketoconazole	fluvoxamine
		nefazodone	gestodene
		saquinavir	imatinib
		telithromycin	mibefradil
			mifepristone
		norfloxacin	amiodarone
		norfluoxetine	NOT azithromycin
		star fruit	chloramphenicol
		voriconazole	ciprofloxacin
			delaviridine
			risperidone
			NOT rosuvastatin
			salmeterol
			sildenafil
			sirolimus
			tamoxifen
			taxol
			terfenadine
			trazodone
			vincristine
			zaleplon
			ziprasidone
			zolpidem

	CYP2C8	CYP3A4/5		
Inducers	rifampin	HIV Antivirals:	glucocorticoids	rifabutin
		efavirenz	modafinil	rifampin
		nevirapine	nevirapine	St. John's wort
		barbiturates	oxcarbazepine	troglitazone
		carbamazepine	phenobarbital	
		efavirenz	phenytoin	
		pioglitazone		

Source: *Flockhart DA. Drug Interactions: Cytochrome P450 Drug Interaction Table. Indiana University School of Medicine (2007). <http://medicine.iupui.edu/clinpharm/ddis/table.asp>. Accessed 04/22/10*

Appendix C – medications card (CUMC)

Note

To the patient:

While no effect has been shown, there is a theoretical possibility that the investigational drug may affect the way some drugs function. Please let the investigator know if you are taking any of the following medications.

If you only know the brand names of the medications you are taking, please discuss this with the study investigator. Please carry this card with you to all appointments with your health care providers while you are in this study.

To health care providers:

No medications need to be discontinued, and doses do not need to be changed. However, specific monitoring for side effects and toxicities will be performed during the study period. Avoid initiating any of these medicines while the patient is on the study. If you have any questions, please contact the principal investigator.

Study Principal Investigator

[name]
Division of Digestive and Liver Diseases
Columbia University Medical Center

[contact] or [contact]
[contact]
E-mail: [contact]

Medications with Possible Drug Interactions

IRB-AAAE9648

Randomized controlled trial of a gastrin-receptor antagonist in Barrett's esophagus

Azole antifungals:

fluconazole
itraconazole
ketoconazole
voriconazole

Benzodiazepines:

diazepam
midazolam
triazolam

Calcium channel inhibitors:

amlodipine
diltiazem
felodipine
nifedipine
nisoldipine
nitrendipine
verapamil

Ergot alkaloids:

dihydro-ergotamine
ergotamine

HIV antivirals:

indinavir
nelfinavir
ritonavir
saquinavir

HMG-CoA reductase inhibitors:

atorvastatin
cerivastatin
lovastatin
simvastatin

Immune modulators:

cyclosporine
sirolimus
tacrolimus

Macrolide antibiotics:

clarithromycin
erythromycin

Steroid 6 β -OH:

estradiol
hydrocortisone
progesterone

Miscellaneous:

barbiturates
carbamazepine
cerivastatin
dofetilide
domperidone
glitazones
glucocorticoids
montelukast
paclitaxel
phenytoin
pimozide
pioglitazone
propranolol
rifampicin
risperidone
salmeterol
sertindole
sildenafil
St John's wort
tamoxifen
trimethoprim

## 1 List of abbreviations

AE	Adverse Event
BE	Barrett's esophagus
BMI	Body Mass Index
BUN	Blood urea nitrogen
CCK2R	Cholecystokinin 2 receptor
CI	Confidence Interval
CgA	Chromogranin A
C max	Peak Plasma Concentration
C trough	Trough Plasma Concentration
CRF	Case Report Form
COX-2	Cyclooxygenase-2
CSR	Clinical Study Report
CV	Coefficient of variance
DCAMKL1	Doublecortin- and Ca 2+ /calmodulin-dependent protein kinase-like protein 1
ECG	Electrocardiogram
ECL	Enterochromaffin-like
HMR	Hammersmith Medicines Research
HR	Heart Rate
ICH	International Conference on Harmonization
IHC	Immunohistochemistry
ITT	Intent-to-treat
LDH	Lactase dehydrogenase
MedDRA	Medical Dictionary for Regulatory Activities
mRNA	Messenger RNA
N	Number of patients
N	Number of observations used in analysis
p53	Tumour protein 53
PK	Pharmacokinetic(s)
PP	Per protocol
PPI	Proton pump inhibitor
PR	Portion of the ECG from the beginning of the P wave to the beginning of the QRS complex, representing atrioventricular node function.
Q1	Lower quartile
Q3	Upper quartile
QRS	The QRS complex of the ECG reflects the rapid depolarization of the right and left ventricles.
qRT-PCR	Quantitative RT-PCR
QT	Portion of the ECG between the onset of the Q wave and the end of the T wave, representing the total time for ventricular depolarization and repolarization.
QTc	Corrected portion of the ECG between the onset of the Q wave and the end of the T wave, representing the total time for ventricular depolarization and repolarization.
QTcB	QTc interval with Bazett's correction method
QTcF	QTc interval with Fridericia's correction method
RBC	Red blood cells

RNAseq	RNA sequencing
RR	Portion of the ECG between consecutive R waves, representing the ventricular rate
RT-PCR	Reverse transcriptase polymerase chain reaction
SAP	Statistical Analysis Plan
SD	Standard deviation
SGOT/AST	Serum glutamic-oxaloacetic transaminase/aspartate amino transferase
SGPT/ALT	Serum glutamicpyruvic transaminase/ alanine aminotransferase
TEAE	Treatment Emergent Adverse Event
WBC	White blood cells
$\Delta$ Ki67	Change in Ki67 expression

### **3 Introduction**

This Statistical Analysis Plan (SAP) is based on the current trial protocol (version 24, 26 April 2018). Where statistical methods differ substantially between this SAP and the protocol, that will be identified in this document.

This SAP describes the datasets and the statistical methods to be used for the reporting and analysis of all data collected during the trial except the efficacy data which will be reported separately. Serum gastrin and plasma CgA data will be included in this SAP.

The randomisation code will not be broken before this SAP is finalised. If a future protocol amendment necessitates a substantial change to the statistical analysis of the trial data, this SAP will be amended accordingly. If, after database lock, additional analyses are required to supplement the planned analyses described in this SAP, those unplanned analyses will not be described in an amended SAP, but they will be identified in the integrated clinical study report (CSR). Any deviations from this SAP will be documented in the CSR.

This SAP has been written in consideration of the following guidelines:

- International Conference on Harmonization (ICH) E9, Guidance for Industry: Statistical Principles for Clinical Trials (ICH E9 1998); and
- ICH E3, Guidance for Industry: Structure and Content of Clinical Study Reports (ICH E3 1995).

Statistical analysis will be done using SAS® 9.3 on a Windows PC.

### **4 Study Objectives and Endpoints**

#### **4.1 Study Objectives**

##### **4.1.1 Primary Objective**

The primary objective of this study is to determine if administration of netazepide (a CCK2R antagonist) to patients with Barrett's esophagus (BE) decreases tissue Ki67 expression, a marker of cellular proliferation.

##### **4.1.2 Secondary Objectives**

The secondary objectives are to assess the effects of netazepide on:

- biomarkers potentially associated with esophageal adenocarcinoma, in particular, cyclooxygenase-2 (COX-2), p53, CCK2R and DCAMKL1; and
- fasting serum gastrin, a marker of gastric acid suppression, and plasma chromogranin A (CgA), a marker of ECL cell hyperplasia.

We also aim to determine whether netazepide is safe in patients with BE.

## 4.2 Study Endpoints

### 4.2.1 Primary Endpoints

Change in Ki67 expression ( $\Delta$ Ki67) between baseline (Visit 2) and the Week 12 visit

### 4.2.2 Secondary Endpoints

- Biomarkers
  - Change from baseline at Week 12 in biomarkers potentially associated with esophageal adenocarcinoma, in particular:
    - Change in CCK2R mRNA levels (measured by qRT-PCR)
    - Change in DCAMKL1 expression (measured by IHC)
    - Change in DCAMKL1 mRNA levels (qRT-PCR)
    - Change in COX-2 mRNA levels (qRT-PCR)
    - Change in p53 expression (IHC)
  - Gene expression will be measured using RNA-Seq. Further examination of any changes in expression from baseline may be done using qRT-PCR and IHC
  - Reduction in PPI-induced increase in plasma CgA
  - Increase in PPI-induced hypergastrinaemia
- Safety
  - Vital signs, ECG, physical examination, laboratory safety tests: blood tests: red blood cells (RBC), haemoglobin, haematocrit, platelets, white blood cells (WBC, differential: neutrophils, bands, lymphocytes, monocytes, eosinophils, basophils), sodium, potassium, magnesium, chloride, bicarbonate, creatinine, serum glucose, blood urea nitrogen (BUN), alkaline phosphatase, lactate dehydrogenase (LDH), serum glutamic-oxaloacetic transaminase/aspartate amino transferase (SGOT/AST), serum glutamicpyruvic transaminase/ alanine aminotransferase (SGPT/ALT), total bilirubin, total protein, albumin, calcium, amylase, lipase; and urine tests: pH, specific gravity, protein, glucose, ketones, blood.
  - Change in histology
- Tolerability: assessment of adverse events.
- Pharmacokinetics: trough and peak concentration of netazepide

## 4.3 Statistical Hypotheses

No formal statistical testing will be done

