## **10 Treatment Comparisons**

The treatment comparison of interest is active (netazepide) versus placebo.

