### **11.2 Conventions for Summary Statistics and Data Displays**

The minimum set of summary statistics for numeric variables will be: n, mean, standard deviation (or standard error), median, minimum, and maximum. 95% confidence intervals will be presented where appropriate for data interpretation.

Categorical data will be summarised in frequency tables with n and percentage. Summaries of a categorical variable will include all recorded values.

The minimum and maximum values will be presented with the same number of decimal places as the raw data collected on the CRF (or to 3 significant figures for derived parameters less than 100 and as integers for values more than 99). The mean and percentiles (e.g. median, Q1, and Q3) will be presented using one additional decimal place. The standard deviation and standard error will be presented using two additional decimal places.

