## **15 Efficacy Analyses**

Efficacy data (serum gastrin and CgA) will be summarised using the ITT and PP populations. Summaries based on the PP population will only be produced if there is a difference between the ITT and PP populations

Serum gastrin and plasma CgA data at each planned visit, and change in Serum gastrin and plasma CgA from baseline at each planned post-baseline visit, will be summarised by treatment group and visit. Individual values will be presented by patient

Mean profile plots for serum gastrin and CgA will also be produced. Each plot will contain all results for all subjects in the active and placebo arms

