## **19 ATTACHMENTS**

### **19.1 Table of Contents for Data Display Specifications**

For overall page layout refer to Appendix B.

The numbering in the tables below will take precedence over the numbering in the shells.

The following tables and figures will be produced (templates provided in Section 19.2.1 and 19.2.2):

Table	Description	Population	Source Listing	Template (Shells below)
10.1	Summary of patient disposition	Safety	16.2.1.2 16.2.3.1	T_SD1
10.2.1	Summary of concomitant medications	Safety	16.2.4.2	T_CM1
10.2.2	Summary of medical history: barrett's esophagus	Safety	16.2.4.3	T_MH1
10.2.3	Summary of treatment compliance	Safety	16.2.5.1	T_COMP1
14.1	DEMOGRAPHIC DATA			
14.1	Summary of demographic characteristics	Safety	16.2.4	T_DM1
14.2	PHARMACOKINETIC and EFFICACY			
14.2.1	Summary of netazepide plasma peak and trough concentration data	Safety	16.2.6.1	T_PK1
14.2.2.1	Summary of serum gastrin and plasma CgA data (ITT)	ITT	16.2.6.2	T_EG2
14.2.2.2*	Summary of serum gastrin and plasma CgA data (PP)	PP	16.2.6.2	T_EG2
14.3	SAFETY DATA			
14.3.1.1	Summary of treatment-emergent adverse events	Safety	16.2.7.1	T_AE1
14.3.1.2	Summary of drug-related treatment-emergent adverse events	Safety	16.2.7.1	T_AE1
14.3.2.1	Listing of fatal adverse events	Safety	16.2.7.1	L_AE1_PG
14.3.2.2	Listing of non-fatal serious adverse events	Safety	16.2.7.1	L_AE1_PG
14.3.2.3	Listing of other significant adverse events	Safety	16.2.7.1	L_AE1_PG
14.3.3	Narratives of deaths, other serious and significant adverse events	Safety	-	-
14.3.4	Summary of laboratory values of potential clinical importance	Safety	16.2.8.1, 16.2.8.3	T_LB1
14.3.5.1	Summary of chemistry laboratory values	Safety	16.4	T_LB2
14.3.5.2	Summary of haematology laboratory values	Safety	16.4	T_LB2
14.3.5.3	Summary of urinalysis results	Safety	16.4	T_UR1
14.3.6.1	Summary of vital signs	Safety	16.4	T_VS1
14.3.7.1	Summary of ECG values	Safety	16.4	T_EG2
14.3.7.2	Summary of ECG values and changes in ECG values of potential clinical importance	Safety	16.4	T_EG3

Figure	Description	Population	Source Listing	Template (Shells below)
14.3	SAFETY AND EFFICACY DATA			

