**Template T\_EG2**

Table 14.3.7.xx Summary of ECG Values

Variable (units)	Treatment	Visit	n	Mean	SD	Median	Min	Max	Change from Baseline						
									n	Mean	SD	Median	Min	Max	
Heart Rate (bpm)	Treatment 1 (N=xx)														
	Treatment 2 (N=xx)														
PR Interval (msec)	Treatment 1 (N=xx)														
	Treatment 2 (N=xx)														

Source: Listing 16.2.xx

*Programming notes:* Continued with all treatment groups and time points  
 Do not summarise RR or QRS axis

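### The SAP covers serum gastrin and plasma CgA but commits only to per-arm summaries, and does not declare that it leaves out the between-arm comparison planned in protocol 13.4

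*SAP*

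**What the plan says.** **Protocol.** Section 13.4 lists the change in serum gastrin and plasma CgA among the secondary efficacy variables and has secondary endpoints analysed in the manner of the primary. The primary analysis there is a two-sample t-test between arms, reported with a nominal p-value and a 95% confidence interval for the difference. Section 13.2 sets significance at p ≤ 0.05 without multiplicity adjustment, and requires departures from the planned analyses to be described in the SAP.

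**SAP, scope and aim.** Section 3 sends the other efficacy data to a separate report, but states: "Serum gastrin and plasma CgA data will be included in this SAP". It also undertakes to identify substantial differences from the protocol's methods. Section 4.2.2 keeps both markers as secondary endpoints; the CgA one reads "Reduction in PPI-induced increase in plasma CgA". Section 10 says: "The treatment comparison of interest is active (netazepide) versus placebo".

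**SAP, analysis.** Section 4.3 reads, in full, "No formal statistical testing will be done". Under Section 15, change in the two markers "from baseline at each planned post-baseline visit, will be summarised by treatment group and visit", with individual values and mean plots. Section 19.1 assigns Table 14.2.2.1 (ITT), and 14.2.2.2 (PP) if produced, to shell T_EG2. That shell is laid out for ECG data, and its note on extension reads "Continued with all treatment groups and time points". Section 11.2 adds: "95% confidence intervals will be presented where appropriate for data interpretation".

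**SAP, declared changes.** Section 17 lists one change, the dropped pharmacokinetic analysis set.

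**The concern.** The SAP names active versus placebo as the comparison of interest, yet for the only two efficacy markers it covers it specifies no estimate of that comparison. A report that follows the SAP to the letter need not contain the randomised contrast the protocol planned, and nothing in the SAP tells the reader that it was dropped.

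This bears most on CgA. Protocol 4.2 rests the dose regimen on CgA suppression seen in healthy subjects, and the between-arm CgA change is the matching evidence in patients with Barrett's esophagus. All patients are on a PPI, so a reduction in the PPI-induced rise is naturally judged against placebo, not within one arm.

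There is also a labelling risk. Under SAP 3, analyses added after database lock are identified as unplanned in the study report. If the sponsor later wants this comparison, one that the protocol specified could end up described as unplanned.

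**Working it through.** **1. Are the markers within this SAP?** Yes. The carve-out in SAP 3 could explain the absence of methods for Ki67 and the tissue markers, but gastrin and CgA are expressly kept.

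**2. Planned against specified.**

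| Item | Protocol 13.4 | SAP 4.3, 15, shell T_EG2 |
|---|---|---|
| n, mean, SD, median, min, max per arm | yes | yes, for value and for change |
| Difference between arms | yes | not specified |
| 95% CI for the difference | yes | not specified; permitted in general by 11.2 |
| Nominal p-value | yes | excluded by 4.3 |

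**3. Is the departure declared?** Section 4.3 is open about the absence of testing but does not say that this differs from the protocol. Section 17 is silent on it.

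**4. The plan's own figures.** Protocol 13.7 and SAP 8.1 give power for Ki67 with 10 per arm, two-sided 0.05. The noncentrality is difference / (SD × √(2/10)), with 18 degrees of freedom:
- 0.30 / (0.16 × 0.4472) = 4.19, power 97.7% (stated 98%)
- 0.25 / (0.14 × 0.4472) = 3.99, power 96.5% (stated 97%)

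All nine cells of Table 1 reproduce within 2 points on the exact t-test. These figures are not in dispute. They concern Ki67 only; no power is claimed for gastrin or CgA.

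**5. Size of the missing interval.** The documents give no SD for change in gastrin or CgA, so the result is in SD units. It assumes 10 evaluable per arm and equal SDs:
- half-width = t(0.975, 18) × √(2/10) = 2.101 × 0.4472 = 0.94 SD of the change
- detectable difference by the same t-test: 1.32 SD at 80% power, 1.53 SD at 90% power

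**6. Can a reader recover it?** Yes. T_EG2 prints n, mean and SD of change by arm and visit. With d the difference in mean change and s² = [(n₁−1)s₁² + (n₂−1)s₂²] / (n₁+n₂−2), the interval is d ± t × s × √(1/n₁ + 1/n₂), and the p-value follows from the same quantities. Apart from rounding, this is the protocol's t-test.

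**7. Which time point?** Protocol 1.9 puts the change in these markers at Week 12; protocol 13.4 says Visit 5. Shell T_PK1 labels the two PK visits Visits 3 and 4, and the schedule in protocol 8.1 takes PK blood only at Weeks 6 and 12, so on that numbering Visit 5 would be the follow-up. Against this, protocol 13.4 itself and protocol 4.1 name only baseline and Weeks 6 and 12 for these two markers, although protocol 8.1 and 8.5 also sample them at follow-up. The label is probably a slip.

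**The case against.** The strongest reply is that this is mainly a documentation gap. The ingredients of the comparison are all displayed, individual values are presented, and what is missing is the line that combines them. The planned inference was also light: the protocol's wording is that secondary analyses will be similar to the primary, the p-values are nominal, there is no multiplicity adjustment, and the trial is a 20-patient pilot with no power claim for these markers. All of this stands, and it limits the weight of the point. It does not remove it. An analysis with no between-arm estimate is not similar to a t-test with an interval for the difference, and two documents require the change to be identified.

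Two stronger readings might be inferred, and the documents do not support them.
- *That the SAP rules out the confidence interval.* It does not. Section 4.3 bars formal testing, not estimation; Section 11.2 sets a minimum set of statistics and allows intervals. The interval is uncommitted, not prohibited.
- *That the protocol compares the arms off drug, because Visit 5 is the follow-up.* The sentences in protocol 13.4 and 4.1 that name baseline and Weeks 6 and 12 point the other way. The label also does no harm under the present SAP, which summarises every planned post-baseline visit. It matters only once a single comparison is restored.

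The 0.94 SD figure is also conditional. Withdrawals without imputation, and the possible non-analysis of samples from patients with HIV (protocol 10.3.2), leave the number evaluable open; the interval widens if it falls below 10 per arm.

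**Conclusion.** The point holds as an undeclared departure. For serum gastrin and plasma CgA, the SAP replaces the protocol's between-arm test and interval with a commitment to per-arm summaries only, and Section 17 does not say so. It affects both efficacy markers within this SAP and one table, or two if the PP table is produced. The interval not committed to has a half-width of 0.94 SD of the change, assuming 10 evaluable per arm and equal SDs.

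The weight is moderate. The inference is nominal and secondary, the difference can be derived from the planned output, and no confirmatory conclusion depends on it. The point does not extend to Ki67 or the other tissue markers, which SAP 3 assigns to a separate report. It is worth correcting because it concerns the SAP's own stated comparison of interest and costs very little to put right.

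**What to change.** Amend the SAP, preferably before the randomisation code is broken:

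1. Limit the statement in Section 4.3 to safety and PK data.
2. In Section 15 and Table 14.2.2.1 (and 14.2.2.2 if produced), add the between-arm difference in change from baseline at Week 12 for serum gastrin and plasma CgA, with 95% confidence interval and nominal p-value.
3. Reconcile Visit 5 in protocol 13.4 with Week 12 in protocol 1.9, so that the restored comparison has one stated time point.

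If the sponsor prefers to keep these markers descriptive, Section 17 should declare that as a change from protocol 13.4 and give the reason.

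The cost is a wording change and extra rows in one or two tables, or a single entry in Section 17. No new data are needed and patients are not affected.
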